- **9. Selection**: Subject eligibility will first be assessed via telephone screening and if records are available, by a preliminary medical record review. If the subject seems to be a likely candidate for inclusion in this protocol, he or she will be evaluated for study eligibility in person. Telephone screens will occur by experienced research personnel adept with this process. Following a face-to-face evaluation and discussion with the research team, an experienced study investigator will determine suitability for enrollment.
- 10. Recruitment: Subjects will be recruited through flyers, public advertisement (newspaper, radio, internet posting), by word of mouth, contact with community service groups, our local IRB-approved screening protocol (KW0003), and clinics and local treatment facilities (e.g., VA Hospital, Community-Based Outpatient Clinics, local private practices). Subjects will be identified via their response to advertisements and/or internal recruiting through the research clinics. Subjects will be asked to call us at the number provided on the flyers if they are interested in participating in the research study. Subjects will be contacted for follow-up appointments via the most convenient means and personal preference, e.g. telephone. All available research staff is responsible for recruiting potential subjects.
- 11. Research Plan: This study will be conducted at the VA Hospital, West Haven, CT.

Overview: This is a diagnosis-informed study designed to provide preliminary data regarding the efficacy and tolerability of riluzole to treat symptoms of PTSD. Subjects diagnosed with PTSD will receive riluzole, 50 mg taken twice daily (BID) for 12 weeks. PTSD subjects will be followed closely on a weekly basis and their liver function and pregnancy tests will be repeated (see Table 1).

Dosing: Following confirmation of eligibility, the dosing regimen for the first week of study medication is 50 mg twice a day (BID). Subjects who are unable to tolerate the study medication will be allowed to take a lower dose. For these subjects, the dose may be lowered to 50 mg taken once a day (QD). Subjects who are unable to tolerate the once a day 50 mg (QD) dosing regimen will be discontinued from the study. Riluzole should be taken 1 hour before or 2 hours after a meal to avoid food-related decreases in bioavailability.

A schedule of the study events is provided in Table 1.

Figure 1. Study Design

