- A. Participants: Twenty patients with a current diagnosis of PTSD or sub-threshold PTSD between the ages of 18-75 will complete the treatment phase of the study. Subjects will initially be pre-screened by phone interview and a preliminary medical record review. Eligible subjects will then be invited for an in-office visit and will complete the written informed consent process. Subjects will be thoroughly screened for inclusion and exclusion criteria as described below.
- B. Discontinuation of subjects: Subjects may be discontinued from study treatment and assessments at any time. Specific reasons for discontinuing a subject from this study are:
  - Voluntary discontinuation by the subject, who is at any time free to discontinue his/her participation in the study without prejudice to further treatment;
  - Clinical deterioration: The following are objective criteria for clinical deterioration, (1) a 35% increase in CAPS scores at any time during the study, (2) Patients with a CGI-I score ≥ 6 at any post-baseline visit, and (3) the onset of active suicidality as assessed by the study investigator or by scoring 5 or more on the item-10 of MADRS;
  - Evidence of neutropenia (ANC ≤ 1500) or other intolerable adverse reaction, or unable to tolerate study drug;
  - Transaminase levels > 5x ULN;
  - Safety reasons as judged by the investigator;
  - Stopping birth control or positive pregnancy test;
  - Evidence of illicit drug abuse (except for cannabis) or problematic alcohol use during trial;
  - Non-compliance to protocol as judged by the investigator; Subjects who do not take between 75-125% of study medication for two consecutive visits are considered non-adherent and are withdrawn from the study medication.

A subject that prematurely discontinues (i.e. stops study medication or no longer wishes to participate) will always be asked about the reason(s) for discontinuation and the presence of any adverse events. If possible, they will be seen and assessed by the investigator. Adverse events will be followed up as medically necessary.

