- 19. Systematic Assessment for Treatment Emergent Events (SAFTEE): The SAFTEE is a commonly used instrument originally developed by NIMH and adapted into a self-report instrument. It examines, in systematic fashion, possible treatment-emergent side effects and probes for specific adverse symptoms, including suicidal thoughts and behaviors, and self-injurious behavior.
- 20. Drug Attitude Inventory- (DAI): The DAI evaluates how attitudes about medications may affect treatment adherence. The items with the most potential for discrimination between dosing compliance and noncompliance are related to subjective 'feeling' factors.
- 21. Perceived Stress Scale (PSS): This is a 10-item self-report questionnaire to assess the severity of perceived stress over the past month.
- 22. Cumulative Adversity Interview (CAI): A multifaceted semi-structured assessment of stressful life events and chronic subjective stress used in research on stress and psychopathology.

Due to the potential of Riluzole to cause elevations in serum aminotransferase levels, liver function tests will be reviewed and monitored for medical significance (marking NCS for results not clinically significant) by the PI, a co-investigator or other medical research personnel (A.P.R.N., R.N. etc.). If any liver transaminase level is > 5X the UNL, the study investigator will be informed and the patient will be discontinued from the study, with appropriate medical follow-up.

PTSD subjects receiving the study medication will be seen weekly. Compliance with study medication will also be assessed weekly and at each visit. Subjects will be given medication diary cards to record the medication that they have taken at each daily dosing interval and the medication that was missed at each dosing interval. Drug accountability will then be done between the medication that was returned and the medication recorded as being taken on the diary cards. A subset of the interviews and measures obtained throughout the study will be repeated at a one-month, in person follow-up. This follow-up will be used to evaluate any lasting effects of the treatment, if any.

The presence of any spontaneously reported side effect or adverse event is carefully documented. Reasons for premature discontinuation of study medication, including intolerable side effects, are recorded; however, all willing subjects continue to return for weekly evaluations as if they remain on study medication.

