All concomitant medications taken during the study are also recorded in the paper research chart, along with dosage information and start and stop dates. Medication management and clinical ratings are performed by the study physician/APRN and the clinical rater, respectively.

Subjects who are unable to tolerate the study medication after adjusting the dosing regimen to the lowest dose of 50 mg QD are withdrawn from study medication. Treatment adherence is monitored by pill counts. In order to minimize risks, subjects are advised during the consenting process that if they discontinue the study medication prematurely, the researchers want them to continue study evaluations as if they were still on the study medication for reasons of safety monitoring (i.e. to evaluate the possibility of withdrawal effects from abrupt discontinuation of the study drug, worsening of psychological symptoms or other newly emergent medical symptoms after stopping the study drug). Non-adherent patients are classified as dropouts in the analysis.

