Suicidal Ideation and Imminent Harm: Despite treatment, people with PTSD may get worse. All communications about suicide and threats are taken seriously. It is important to assess the risk of suicide carefully when working with these individuals. Many subjects may admit to fleeting thoughts of death or briefly wishing for death; these thoughts need to be considered in context of the subject's overall history, along with a consideration of other risk factors for suicide. Study clinicians will assess patients at each visit for suicide risk and potential. Individuals at such risk will be treated appropriately, including options such as increased contact, more frequent clinical visits, or emergent psychiatric hospitalization. Subjects who score > 5 on the MADRS item 10 (suicide) at screening will be excluded from the study. In addition, a serious suicide or homicide risk, as assessed by evaluating clinician will be considered an exclusion criterion.

Throughout the study, any subject who scores  $\geq 5$  on the MADRS item number 10 will be discontinued from the study. Any subject with scores of  $\geq 6$  on the CGI-I will be discontinued from the study.

Subjects will be informed of any important discoveries made during this study, which may affect their condition or willingness to participate in this study by leaving a message (with subject permission) to contact the study team or by letter, if the subject cannot be reached by phone.

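### The protocol contradicts itself on whether stopping riluzole also ends study assessments, so CAPS may be lost in subjects removed for worsening

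*Combined protocol and SAP*

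**What the plan says.** All references are to the combined protocol and SAP.

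- **Intolerance.** Section 11, Dosing: "Subjects who are unable to tolerate the once a day 50 mg (QD) dosing regimen will be discontinued from the study". Section 11.C.3, in the text after the list of instruments, says that subjects still intolerant after adjustment to "the lowest dose of 50 mg QD are withdrawn from study medication".
- **After stopping the drug.** Section 11.C.3 records the reasons for stopping and adds that "all willing subjects continue to return for weekly evaluations as if they remain on study medication". It makes no exception by reason. Subjects are told at consent that, if they stop early, "the researchers want them to continue study evaluations as if they were still on the study medication for reasons of safety monitoring".
- **Liver values.** The transaminase paragraph of section 11.C.3 and section 12 (Protection Against Risks) both take a subject above 5 x ULN out of the study.
- **Deterioration.** Section 12 (Suicidal Ideation and Imminent Harm) says a subject scoring 6 or more "on the CGI-I will be discontinued from the study", and says the same for MADRS item 10 at 5 or more. Section 12 (Protection Against Risks) speaks instead of stopping the drug and moving to standard treatment. Section 8 leaves it to a case-by-case decision whether a deteriorating subject stays.
- **General rule.** Section 11.B: "Subjects may be discontinued from study treatment and assessments at any time". A subject who stops early is always asked about reasons and adverse events. Beyond that: "If possible, they will be seen and assessed by the investigator".
- **Measurement and analysis.** Table 1 schedules CAPS after baseline at visit 6, visit 12 and the one-month follow-up, with no early-stop column. MADRS and CGI are taken at every visit. Data Analysis plans an intent-to-treat mixed model of CAPS over time, justified under missing at random, and names no sensitivity analysis for departures from it. Section 11.C.3 classes non-adherent patients as dropouts in the analysis without saying what happens to their data.

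**The concern.** The primary result is the change in CAPS in one arm. If a stopping criterion ends participation, CAPS stops too, and some of these criteria are themselves signs of a poor outcome. CGI-I and MADRS item 10 can trigger removal at any weekly visit, while on-treatment CAPS is taken twice. A subject removed between CAPS visits gives no further CAPS, and one removed before visit 6 gives none after baseline. The worsening that caused removal is then recorded on scales that the CAPS model does not contain. The model would in effect assign such subjects the course of those who stayed. With no control arm, any resulting bias falls directly on the primary estimate.

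**Working it through.** **1. The passages side by side.**

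| Reason for stopping | Text that ends participation | Text that ends medication only, or leaves it open |
|---|---|---|
| Cannot tolerate once-daily dosing | 11, Dosing | 11.C.3: off medication, evaluations continue |
| Transaminases > 5 x ULN | 11.C.3, liver paragraph; 12, Protection Against Risks | 11.C.3, follow-up paragraph, which makes no exception by reason |
| CGI-I >= 6 or MADRS item 10 >= 5 | 11.B list; 12, Suicidal Ideation and Imminent Harm | 12, Protection Against Risks: drug stopped; 8: case by case; 11.C.3 follow-up paragraph |
| Non-adherence | 11.B, by its place in the list | 11.B, same bullet: off medication |

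The conflict is direct for intolerance. For liver values and deterioration it comes from setting specific removal rules against a general keep-attending rule.

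**2. Which removals threaten missing at random.**

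- *A 35% rise in CAPS (11.B).* The trigger is an observed CAPS value that is in the model. Later loss can be missing at random.
- *CGI-I or MADRS item 10.* The trigger is outside a model of CAPS on time. Loss depends on worsening that CAPS may not yet have recorded, so the assumption can fail, in the direction of apparent improvement.
- *Intolerance.* This is also outside the model. Its link to CAPS is unknown.
- *Liver values.* Section 12 reports 2% above 5 x ULN in ALS patients. Expected cases are 0.02 x 20 = 0.4 or 0.02 x 50 = 1.0. The chance of at least one is 1 - 0.98^20 = 33% or 1 - 0.98^50 = 64%. These subjects need not be the worst on CAPS.

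**3. The plan's own figures.** There is no effect size, SD, power or dropout rate to reproduce. Section 7 gives about 50 enrolled for 20 completers. That implies 1 - 20/50 = 60% loss, and 20/(1 - 0.6) = 50. It mixes screen failure with dropout, so it is not a removal rate.

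**4. Illustrative size.** All inputs here are assumptions: true mean change 0, and SD of the 12-week change 10 points unless stated.

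- *Removal when a noisy weekly signal of change passes a threshold* (random slope plus AR(1), visit 6 CAPS kept if the subject is still in, missing-at-random estimate at week 12):
  - 7.2% removed gives -0.67 points, 14.6% gives -1.26 and 21.6% gives -1.78.
  - A repeat with AR(1) correlation 0.8 and a slope share of variance of 50% to 90% gave about -0.8, -1.5 and -1.9 at 7% to 7.5%, 15% and 21% removed.
  - A further run with another variance split gave -0.8 to -2.4.
- *A different model* (random-intercept mixed model, n = 50, SD of observed change sqrt(8^2 + 5^2 + 5^2) = 10.7, all post-baseline CAPS lost in those removed): -1.3 at 10% removed and -2.3 at 20%. With CAPS kept it gave -0.01.
- *Extreme case*, where exactly the worst fraction p at week 12 is lost and no CAPS is obtained: the bias is phi(z)/(1 - p) SD, with z the upper-p normal quantile. This is 0.109, 0.195 and 0.350 SD for p = 5%, 10% and 20%, or 1.1, 2.0 and 3.5 points.

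**5. Against sampling error.** With SD 10, the standard error of the mean change is 10/sqrt(20) = 2.24 for 20 subjects and 10/sqrt(50) = 1.41 for 50. A bias of 0.7 to 2 points is 0.3 to 0.9 standard errors at 20 and 0.5 to 1.4 at 50.

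**The case against.** The strongest reply is that this is loose wording. Section 11.B itself explains early discontinuation as either stopping medication or no longer wishing to take part. The specific follow-up text in section 11.C.3 keeps willing subjects in evaluation whatever the reason. On that reading nothing is lost. The trial is also an open-label, uncontrolled pilot seeking early signals, where change cannot be attributed to the drug even with complete data.

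Part of this stands, and it limits the severity. It does not remove the point. Section 11.B uses both terms in one list and expressly lets assessments end with treatment, so a reader cannot tell which rule governs. The stated purpose of continued evaluation is safety monitoring, so it is not certain that CAPS is included. CAPS that was never taken cannot be recovered at analysis.

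A reader might go further in several ways that the documents do not support:

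- *That every early stop loses the worst-faring subjects.* Liver exits would be few and are not selected on CAPS.
- *That missing at random must fail.* Removal on an observed CAPS rise can satisfy it.
- *That removals would mostly precede any post-baseline CAPS.* No timing is given. In one assumed model only 10% to 43% of removals fell by week 6.
- *That different sites would apply different passages.* The study has one site. The risk is inconsistency between staff over a 5-year study.
- *That safety follow-up disappears.* Section 11.B follows adverse events, and section 12 follows subjects until symptoms resolve when treatment ends for physical risk.
- *That full follow-up would remove all bias.* Worsened subjects move to standard treatment. If that lowered CAPS by an assumed 10 points in 7% to 22% of subjects, the mean would shift by 0.07 x 10 = 0.7 to 0.22 x 10 = 2.2 points, which is of similar size.

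**Conclusion.** The contradiction is in the current text and reaches the primary endpoint. Under the reading that stopping ends participation, subjects removed for deterioration on weekly non-CAPS signals give no further CAPS. The missing-at-random justification does not cover that loss, and the bias favours riluzole.

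Only the direction follows from the design. The size of roughly 0.7 to 2 CAPS points rests on an assumed SD of change of 10, 7% to 22% removed for worsening, and removal driven by a noisy signal of that worsening. None of these comes from the documents. Intolerance may add to the bias, but nothing here quantifies it. Should-fix: the gap is real and cheap to close, but it does not by itself decide how an uncontrolled pilot is read.

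**What to change.** 1. **Reconcile** section 8, section 11 (Dosing, B and C.3) and section 12 (Protection Against Risks; Suicidal Ideation and Imminent Harm). For each stopping reason, state in one way whether stopping medication also ends study assessments. The stopping rules, and the investigator's discretion to end assessments for safety, are for the sponsor to settle. A reader might infer that only withdrawal of consent should end assessments. Section 11.B says otherwise, and this point does not ask to override it.
2. **Collect CAPS.** Add an early-stop CAPS to Table 1 for subjects who agree. Keep the visit 6, visit 12 and one-month CAPS for willing subjects who remain in follow-up under section 11.C.3.
3. **Specify the analysis.** Say how CAPS taken after stopping the drug or starting other treatment enters the intent-to-treat model. Reconcile this with the section 11.C.3 statement that classes non-adherent patients as dropouts.

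Cost: protocol wording, one Table 1 column, about one hour of CAPS rating per interview (the duration given in section 11.C.3) by existing raters, and some extra visit payments at the $50 rate in section 17. The downside is that post-stop CAPS may include the effect of other treatment, which is why step 3 is needed.

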#### **Data Analysis**

Descriptive statistics will be calculated prior to statistical analysis. Distributions of quantitative variables will be assessed for normality using normal probability plots and Kolmogorov-Smirnov statistics and transformations or non-parametric methods will be used as necessary. All statistical tests will be two-sided. Uncorrected alpha level of 0.05 will be used for testing the primary hypothesis. Pairwise post-hoc comparisons and tests of secondary outcome measures will be adjusted using Holm-Bonferroni procedure. All analyses will be intent-to-treat. We will using mixed effects regression models, with time effects for the primary outcome variable (CAPS). We do not expect significant moderating effects of alcohol use comorbidity but will assess the interaction between treatment and alcohol use comorbidity and perform follow-up tests as necessary. This approach will be applied to most secondary outcome measures as well. Mixed effects regression models use all available data on each subject, are flexible in modeling the correlation structure of the data and give unbiased results under missing at random

assumptions. In addition to testing the potential moderating effect of comorbid alcohol use described above, we will also perform exploratory analyses to the assess moderating effects of depression, medication status, substance abuse, age, and gender by adding these factors one at a time to the models above and testing interactions between each potential moderator and treatment group. Effects of intermittent missing data due to noncompliance with treatment schedule can also be assessed.

Table 1. Schedule of Study Events\*\*

	1 doie 1. Senedule of Study Events											
Visit	Screeni ng a	Baselin e	1	2&3	4	5,6,&7	8	9,10,11	12	month follow- up		
Day	0	0	7	14&21	28	35,42, & 49	56	63, 70, &77	84	114		
Informed Consent b	X											
Demographics	X											
SCID / MINI	X											
C-SSRS baseline	X											
MGH ATRQ	X											
ETI-SR, KLS, GPELS, CES	X											
M-MACE	X											
Psychiatric Evaluation	X											
BP, Pulse, Resp., Wt., Temp.	X	X	X	X	X	X	X	X	X			
ECG	X											
Physical Exam	X											
СВС	X				X		X		X			
СМР	X				LFTs		LF Ts		LFTs			
Serum Pregnancy (1)/ Urine Pregnancy (2)	X(1)	X (2)			X(2)		X( 2)		X(2)			
Urinalysis	X											
Inclusion/Exclusion	X											
CAPS	X	X °				X (visit 6 only)			X	X		
MADRS	X	X	X	X	X	X	X	X	X	X		
PCL, QIDS-SR, PSWQ, PSQI, SDS, SAFTEE		X	X	X	X	X	X	X	X	X		

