Protection Against Risks: All clinical raters have experience in clinical psychiatric assessment and will make every effort to implement protocol procedures in a sensitive and supportive manner. Research interviews will be interrupted if subjects become distressed or object to answering questions. Other measures to minimize risks include the careful assessment of each subject before the study, and close clinical scrutiny during all aspects of the study. Screening for suicide risk factors and suicidality is described in the research design.

Weekly contact is maintained throughout the clinical trial. A study staff member will call participants, during any week in which there is no clinic visits, to help ensure subject safety and protocol adherence.

We have included safety measures such as discontinuation of the study drug and transition to standard clinical treatment should subjects worsen to a sufficient degree. These precautions are likely to be highly effective in minimizing risks. Subjects may be hospitalized if they have a worsening of their symptoms, including becoming suicidal. In this case or if subjects discontinue study medication they will receive standard short-term clinical treatment as indicated.

Due to the potential of riluzole to cause elevations in serum aminotransferase levels, subjects will have liver function tests performed prior to initiating the trial and monthly for the duration of the study, or more frequently if clinically indicated. Patients with any evidence of clinically significant liver abnormalities or any liver transaminase level > 1.5 x ULN at baseline will be excluded from the study. Subjects will be discontinued from the study if any LFT measure rises above 5 x the ULN once treatment has been initiated. This is the recommendation in the PDR and is what has been used in previous studies. If treatment is terminated due to physical risks, subjects will be followed carefully until resolution of symptoms and treated with the follow up care described in the protocol.

Subjects will also be asked to report any cough, difficulty breathing or chills to the study staff in order to monitor for the possible emergence of interstitial lung disease or hypersensitivity pneumonitis. The study investigator, physician/APRN, and rater ask patients about any new symptoms at every visit.

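### The plan is inconsistent on whether a subject who cannot tolerate once-daily riluzole stays in assessment, and on whether CAPS scores taken after stopping enter the intent-to-treat model

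*Combined protocol and SAP*

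**What the plan says.** Section 11, under Dosing, allows a step down from 50 mg twice daily to once daily and then states: "Subjects who are unable to tolerate the once a day 50 mg (QD) dosing regimen will be discontinued from the study". Section 11.B points the same way. It opens with "Subjects may be discontinued from study treatment and assessments at any time", and its reasons for leaving the study include "other intolerable adverse reaction, or unable to tolerate study drug". Transaminases above 5 x ULN are handled alike in 11.B, in 11.C and in section 12 under Protection Against Risks: "Subjects will be discontinued from the study if any LFT measure rises above 5 x the ULN once treatment has been initiated".

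The later text of 11.C treats the same event differently. Subjects who cannot tolerate the drug "after adjusting the dosing regimen to the lowest dose of 50 mg QD are withdrawn from study medication". At consent, subjects are told that if they stop early "the researchers want them to continue study evaluations as if they were still on the study medication"; the reason given is safety monitoring. On premature stopping, with intolerable side effects named as a reason, 11.C says "all willing subjects continue to return for weekly evaluations as if they remain on study medication".

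Section 11.C then classes non-adherent patients as dropouts in the analysis. Section 11.B defines non-adherence as taking outside 75-125% of medication for two consecutive visits.

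Data Analysis says "All analyses will be intent-to-treat" and specifies a mixed model that uses every available observation and is unbiased under missing at random. It does not say whether CAPS obtained after stopping riluzole is included. After baseline, Table 1 schedules CAPS at visit 6, visit 12 and the one-month follow-up only.

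**The concern.** There are two inconsistencies, and both affect the primary outcome. The first is about attendance: staff reading Dosing and 11.B could end assessments for a subject whom staff reading 11.C would keep. The second is about analysis: even if that subject attends every visit, someone off drug arguably meets the non-adherence definition, and the dropout sentence could then be used to set the off-drug CAPS aside.

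With only two CAPS assessments between baseline and week 12, one early stop can remove all of a subject's post-baseline data. There is no control arm, so Aim 1 is the mean change itself, and a shift in who is measured passes straight into the estimate. Under one handling the result describes everyone dosed. Under the other it describes those who tolerated the drug, yet it would still be labelled intent-to-treat. Section 6 says the pilot will inform larger controlled studies, whose designers need to know which quantity they have.

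**Working it through.** **The plan's own figures.** There is nothing to reproduce: the documents give no power, effect size, SD or intolerance rate. Section 7 plans about 50 enrolled for 20 completers, a combined loss of 1 - 20/50 = 60%. This is not split between screening failure and dropout, so no stopping rate can be drawn from it.

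**Step 1. What each reading yields for a subject who stops before visit 6.**

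| Handling | CAPS at visits 6 and 12 | In the model? | Week-12 change describes |
|---|---|---|---|
| Leaves the study | Not collected | No | Those who tolerated riluzole |
| Stays, but data set aside as a dropout's | Collected if willing | No | Those who tolerated riluzole |
| Stays, data used | Collected if willing | Yes | All dosed subjects, on or off drug |

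In the first two rows the missing-at-random model in effect fills the gap from subjects who stayed on drug.

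**Step 2. Arithmetic; all inputs assumed.** Let q be the share of dosed subjects who stop before visit 6, D the on-drug week-12 change and d the off-drug change.

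- Data absent or set aside: estimate = D.
- Data used: estimate = (1 - q)D + qd.
- Gap = q(d - D).

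Take D = -10, with 20 completers plus 2, 5 or 9 early stoppers who all return for CAPS.

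| Stoppers / dosed | q | Absent or set aside | Used, d = 0 | Used, d = -5 |
|---|---|---|---|---|
| 2 / 22 | 9.1% | -10.0 | -9.1 | -9.5 |
| 5 / 25 | 20.0% | -10.0 | -8.0 | -9.0 |
| 9 / 29 | 31.0% | -10.0 | -6.9 | -8.4 |

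The gap runs from about 0.5 (2/22 x 5) to 3.1 (9/29 x 10) points.

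**Step 3. Simulation check.** A random-intercept mixed model (baseline, week 6, week 12) was fitted with the stoppers' later CAPS missing and again with it kept. Assumptions: between-subject SD 9, residual SD 6, 60% of the change reached by week 6, no off-drug improvement, 300 runs per setting.

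| Dosed | True D | Estimate, missing vs kept | Power, missing vs kept |
|---|---|---|---|
| 22 | -10 | -10.1 vs -9.2 | 0.99 vs 0.99 |
| 25 | -10 | -9.8 vs -7.9 | 1.00 vs 0.99 |
| 29 | -10 | -10.0 vs -6.9 | 1.00 vs 1.00 |
| 22 | -5 | -5.1 vs -4.7 | 0.77 vs 0.71 |
| 25 | -5 | -5.0 vs -4.0 | 0.76 vs 0.65 |
| 29 | -5 | -4.9 vs -3.3 | 0.77 vs 0.54 |

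A second simulation (between-subject SD 10, residual SD 7) gave a standard error for the week-12 change of 1.9 to 2.2. The largest gap is thus about 3.1/2.1 = 1.5 standard errors.

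**Step 4. Where the gap vanishes or reverses.** If d = D, the gap is q x 0 = 0. If subjects improve more after stopping, say d = -15 with 5 of 25 stopping, the estimate with data used is 0.8 x (-10) + 0.2 x (-15) = -11.0, larger than -10. This is possible because section 12 offers standard short-term treatment to those who stop.

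**The case against.** The best case for the plan is that it uses leaving the study loosely, to mean stopping the drug. Section 11.B glosses premature discontinuation as either stopping medication or no longer wishing to take part. Its last bullet, under reasons for leaving the study, speaks of withdrawal from medication. The Dosing paragraph is silent on assessments, the opening of 11.B is permissive, and 11.C is the specific text on what follows stopping. This reading is plausible, so a reader who infers two irreconcilable rules goes too far. It does not settle the matter: 11.B names assessments as well as treatment, and its closing paragraph provides only for questions about reasons and adverse events and, if possible, one assessment. It also leaves the dropout sentence unresolved.

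Three other strong inferences are not supported:

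- *That the attendance rule alone decides the CAPS result.* The dropout sentence could exclude off-drug CAPS even with full attendance.
- *That the plan inflates the effect by a known amount, up to 31%.* Every input is assumed. Section 12 describes most side effects as mild, and its adverse-event percentages are not stopping rates. Zero off-drug improvement is an extreme choice for an open-label study.
- *That leaving the study ends safety follow-up.* Section 11.B still asks about adverse events and follows them as medically necessary, and section 12 follows subjects stopped for physical risk until symptoms resolve.

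It is also fair that this is an open-label pilot seeking early signals, with no decision threshold tied to the CAPS estimate.

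**Conclusion.** The concern holds in limited form. The current text gives inconsistent instructions for a subject intolerant of 50 mg once daily, and the dropout classification conflicts with an intent-to-treat analysis of all available data. Applying either the leave-the-study rule or the dropout rule would take early stoppers' post-baseline CAPS out of the model and change what the week-12 figure describes.

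The shift is about 0.5 to 3.1 points if the on-drug change is -10, 9% to 31% stop before visit 6, all of them return, and their off-drug change is 0 or -5. It is zero if the two courses match and can reverse. It alters the chance of significance materially only when the true change is small and the stopping share is large. The plan should be clarified; the point does not invalidate the pilot.

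**What to change.** **Dosing (section 11), and the matching intolerance entry and opening sentence of 11.B.** Suggested wording: *Subjects unable to tolerate 50 mg once daily will stop study medication and will be asked to complete the remaining scheduled assessments, including CAPS at visits 6 and 12, if willing and unless the investigator judges this unsafe.* Use the same wording for the transaminase rule in 11.B, 11.C and section 12. The safety clause keeps the investigator's discretion, for example in active suicidality.

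**Section 11.C and Data Analysis.** Suggested wording: *The primary CAPS model includes all subjects who take at least one dose and all CAPS through visit 12, on or off riluzole. Dropout describes treatment status and does not exclude data. A supporting analysis uses only CAPS obtained on riluzole.*

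**Cost.** A few sentences, with no visits or tests beyond those 11.C already requests. The primary estimate may be less favourable than the on-drug one. Some subjects who stop will decline to return, so some CAPS will still be missing.
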